### 7.2.1. Definition of the Adverse Event Reporting Period

The AE reporting period for safety surveillance begins when the subject provides written consent and continues until either 90 days after the last dose of study drug or the start of new anticancer treatment, whichever comes first. Following the End-of-Treatment Safety Follow-up Visit, only treatment-related AEs will be documented through the Treatment Follow-up Period of up to 12 months after the last dose of study drug or until disease progression and/or initiation of a new line of therapy, whichever comes first.

Any SAE suspected to be related to trial treatment must be reported whenever it occurs, irrespective of time elapsed since last dose of study drug.

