#### **8.3.4.1. Adverse Events**

Adverse events will be coded according to Medical Dictionary for Regulatory Activities (MedDRA) version 21.0. Severity of AEs will be graded using CTCAE (version 4.03) toxicity grading scale whenever possible.

Treatment-emergent AEs are AEs with onset dates during the on-treatment period, or the worsening of an event during the on-treatment period. Incidence of TEAEs, regardless of attribution, and AEs defined as related to AGEN2034 will be summarized by system organ class and preferred term, and described in terms of severity and relationship to AGEN2034.

Analysis of AES will be performed for events that are considered as treatment emergent. Adverse events leading to death or discontinuation of trial treatment, events with CTCAE Grade 3 or higher, study drug-related events, and SAEs will be summarized.

Indications of dose-related ADRs will also be examined.

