5.4. DEFINITION OF AN EXTENDED ON-TREATMENT PERIOD

Extended on-treatment period (follow-up) is defined as the time from the first dose of study treatment through 90 days after the last dose of study treatment or end of study, whichever occurs first. This is used for reporting immune-related AEs and also as a sensitivity analysis for reporting all treatment emergent adverse events.

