7.6.2. Adverse Events

Adverse events (AEs) will be coded using MedDRA v22.1 or later and will be classified by SOC and PT.

Severity of AEs will be assessed by investigators according to NCI-CTCAE v4.03, and AEs will be classified by the investigator as either related or not related to study drug

Pre-existing conditions are those that started before and continued after signing of informed consent. Prior AEs (non-treatment emergent) are those occurring after the subject signed the informed consent and before the administration of the first dose of study treatment. Immune-related AEs will be evaluated in the extended on-treatment period to account for late toxicities. A separate listing will be provided for AEs incurred after on-treatment period.

TEAEs are AEs with onset during or after administration of first dose, or the worsening of a pre-existing condition during the on-treatment period. Immune-related AEs will be considered TEAEs during the extended on-treatment period. In a sensitivity analysis, TEAEs will be defined as AEs with onset during or after administration of first dose, or the worsening of a pre-existing condition during the extended on-treatment period. A separate listing will be provided of all AEs with onset date, or worsening date between end of “On-treatment period” (35 days) and end of “Extended on-treatment period” (90 days).

Any missing onset date, causality, or severity must be queried for resolution. Unresolved / missing causality and severity will be handled according to the following rules:

- An unresolved causality will be considered treatment-related
- An unresolved severity will be identified as an unknown severity

AEs with partial dates will be considered TEAEs unless the AE can unequivocally be determined as not treatment emergent.

The following AEs are considered as AEs of special interest (AESIs):

- Infusion-related reactions per definition in NCI-CTCAE v4.03 specification (*per investigator assessment*)
- Lab-based hepatic toxicity: An elevated aspartate transaminase (AST) or alanine transaminase (ALT) lab value \geq to $3 \times$ upper limit of normal (ULN) with a corresponding elevated total bilirubin value $\geq 2 \times$ ULN, at the same time, an alkaline phosphatase lab value $< 2 \times$ ULN, as determined by way of protocol-specified laboratory testing or unscheduled laboratory testing
- Any AE suspected to be immune-mediated (i.e. an irAE) by the investigator

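### SAP 7.6.2 sets no end date for new-onset TEAEs, so as worded the 35-day and 90-day analyses give the same count for AEs that are not immune-related

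*SAP*

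**What the plan says.** **Main definition, SAP 7.6.2.** "TEAEs are AEs with onset during or after administration of first dose, or the worsening of a pre-existing condition during the on-treatment period".

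**Sensitivity definition, SAP 7.6.2.** The onset clause is identical: "TEAEs will be defined as AEs with onset during or after administration of first dose". Only the period attached to worsening changes, from the on-treatment period to the extended one.

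**The periods.** SAP 5.3 ends the on-treatment period 35 days after the last dose, and SAP 5.4 ends the extended period at 90 days. Both stop sooner if the study ends. SAP 5.4 gives the extended period two uses: immune-related AEs (irAEs), and "also as a sensitivity analysis for reporting all treatment emergent adverse events".

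**Other SAP 7.6.2 rules.** "Immune-related AEs will be considered TEAEs during the extended on-treatment period". Also: "A separate listing will be provided for AEs incurred after on-treatment period". A further listing covers AEs starting or worsening between the 35-day and 90-day limits.

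**Protocol 8.3.4.1.** "Treatment-emergent AEs are AEs with onset dates during the on-treatment period, or the worsening of an event during the on-treatment period". Protocol 8.3.4 ends that period 30 days after the last dose, or the day before a new anticancer therapy if that is sooner.

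**Collection, Protocol 7.2.1.** All AEs are in the reporting period until 90 days after the last dose or the start of new anticancer treatment. The next sentence says that, once the safety visit is past, "only treatment-related AEs will be documented through the Treatment Follow-up Period of up to 12 months after the last dose of study drug", ending at progression or a new line of therapy.

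**The concern.** The protocol puts a time limit on both routes to treatment emergence. The SAP rewrote the onset route with a start and no end, and left the limit on worsening only. SAP 4.1, which summarises changes from the protocol, does not mention it.

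The TEAE flag matters because the frequency, severity and duration of TEAEs is a secondary endpoint (SAP 3.5) and the flag feeds most of the AE tables in SAP 7.6.2. Two things are at stake. First, two programmers could defend different flags from the same text. Second, the 90-day sensitivity analysis is there to show whether the 35-day cut-off matters. If onset has no limit in either definition, the analysis cannot show this for new-onset AEs outside the irAE rule.

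**Working it through.** Neither document states a figure that depends on this definition, so there is nothing to reproduce. The check applies each rule to the same event.

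**Inputs.** Main limit 35 days (SAP 5.3); extended limit 90 days (SAP 5.4); protocol limit 30 days (Protocol 8.3.4); related-AE collection up to 12 months (Protocol 7.2.1), taken as 365 days. The event is a new-onset AE, not an irAE, in a subject still on study with no progression and no new therapy.

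**Is it a TEAE?**

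| Onset, days after last dose | SAP 7.6.2 as worded (main / sensitivity) | Onset bounded by SAP 5.3 / 5.4 (main / sensitivity) | Protocol 8.3.4 |
|---|---|---|---|
| 20 | yes / yes | yes / yes | yes |
| 32, 35 | yes / yes | yes / yes | no |
| 60, 90 | yes / yes | no / yes | no |
| 91, 180, 365 | yes / yes | no / no | no |

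**Difference between the two analyses.** With onset bounded, they differ by events starting on days 36 to 90, a span of 90 − 35 = 55 days. As worded, they differ by no new-onset events, only through worsening of pre-existing conditions.

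**Illustration.** Three subjects each have one related, non-immune AE, at 20, 60 and 200 days after last dose. Main / sensitivity counts are 3 / 3 as worded and 1 / 2 with onset bounded. The protocol rule gives 1.

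**irAEs.** They have their own 90-day rule. If that specific rule governs, three irAEs on the same days give 2 / 2 (days 20 and 60 count, day 200 does not). The defect therefore concerns AEs outside the irAE rule.

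**Which late events could enter the data.**
- From the safety visit to day 90, the protocol conflicts with itself. Section 7.2.1 and footnote 5 of Table 13 each set a 90-day period for all AEs, then restrict documentation after the safety visit to related AEs.
- After day 90, only related AEs are collected, for at most another 365 − 90 = 275 days and ending at progression or new therapy. Related SAEs are reportable at any time (Protocol 7.2.1).

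**The case against.** The strongest answer is that nobody reading the whole SAP would leave onset open. Two periods are defined, SAP 5.4 says what the longer one is for, and the irAE rule would be redundant if onset had no limit. AEs after the on-treatment period are listed separately, and so are those between the two limits. The immune-mediated clusters are also confined to the extended period. The phrase naming the period could be read as covering both clauses, although the comma favours the narrower reading. The listing between the limits also shows the very events by which the windows differ.

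Most of this stands, and it establishes the intent. It does not repair the definition. The flag is programmed from that sentence, the sensitivity sentence repeats the same open clause, and a listing is not the promised re-tabulation of TEAEs.

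A reader might go further and infer that the plan counts AEs up to a year after treatment as TEAEs, inflating the drug-related proportion. The documents do not support that. The surrounding text points to a bounded window, irAEs stop at 90 days under their own rule, and related-AE collection ends at progression or new therapy. Whether unrelated AEs are recorded between the safety visit and day 90 is itself unclear. After day 90 the asymmetry is real under the literal reading, but no document gives the number of such events.

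**Conclusion.** The point holds as a drafting inconsistency in an operative definition. Read literally, SAP 7.6.2 has no upper time limit for new-onset AEs that are not irAEs, and its main and sensitivity analyses give identical counts for them. That contradicts Protocol 8.3.4.1 and the SAP's own evident intent, and SAP 4.1 does not declare it.

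The size in events cannot be stated. In time, the sensitivity analysis loses the 55-day contrast it was meant to test. Events admitted after day 90 would be treatment-related only. The conclusion assumes that the sentence is applied as punctuated and that the specific irAE rule takes precedence over the general one. The matter is minor, but worth correcting because the flag runs through the safety tables.

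A related mismatch remains even with onset bounded: the SAP period is 35 days with no stop at new therapy, whereas the protocol period is 30 days and stops the day before new therapy. An AE on day 32 or 35 is a TEAE under one and not under the other.

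**What to change.** In SAP 7.6.2, put the limit on both clauses:
- **Main analysis:** onset or worsening on or after first dose and no later than the end of the on-treatment period in SAP 5.3.
- **irAEs and the sensitivity analysis:** the same wording with the extended period in SAP 5.4.
- **Later AEs:** listed separately, as already planned.

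Then reconcile SAP 5.3 with Protocol 8.3.4 on the length of the period and the stop at new anticancer therapy, or record the difference in SAP 4.1. State also how AEs between the safety visit and day 90 are treated, given the conflict within Protocol 7.2.1 and footnote 5 of Table 13.

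The cost is SAP wording and an explicit upper date in the two flag derivations. No new data are needed.

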5.3. DEFINITION OF ON-TREATMENT PERIOD

On-treatment period is defined as the time from the first dose of study treatment until the end of treatment safety follow-up (4 weeks \pm 7 days from the last dose of study drug, i.e., until 35 days from the last dose) or end of study, whichever occurs first.

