7.6. SAFETY ANALYSIS

7.6.1. Drug Exposure

Balstilimab is administered intravenously (IV) every 2 weeks (Q2W).

Overall drug exposure will be summarized in Safety Analysis Set by the following parameters:

- Duration of treatment (week), calculated as: (last dose date – first dose date + 1)/7
- Number of balstilimab infusions received
- Total cumulative dose (mg), defined as the sum of the actual doses (mg) taken
- Dose compliance, defined as percentage of patients with any actual dose higher than 10%, 15%, or 20% or lower than 10%, 15%, or 20% relative to planned dose as entered on eCRF (Note: pharmacy manual specified that dose does not need to be adjusted for weight changes within 10%)

- Number of doses with infusion related reactions (as reported on drug administration eCRFs)
- Occurrences and number of actual doses exceeding adjusted planned dose by more than 5% (adjusting for up to 10 % weight loss.)

Per pharmacy manual, no adjustment in dose was required for body weight changes within 10%, therefore dose exceeding planned dose by $> 5\%$ will be interpreted as any dose 5% greater than the highest daily dose prescribed by the clinical trial protocol, after accounting for up to 10% changes due to decrease in body weight. Adjusted planned dose is calculated by multiplying prescribed dose level by adjusted weight W_{adj} . Denoting by W_0 and W the baseline and the most recent weights, adjusted weight is: $W_{adj} = W$ for $W \geq W_0$ and $W_{adj} = \min(W_0, 1.1 \times W)$ for $W < W_0$.

- Subjects with any dose interrupted/not completed
- Number of doses interrupted/not completed

Missing weight measurements in drug exposure analysis will be imputed by last observation carried forward, multiple measurements for the same timepoint will be averaged.

Details of study treatment exposure will be listed for Safety Analysis Set.

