Unless otherwise stated, the number of subjects with an event (subject-wise) and the number of events (event-wise) will be provided for each summary.

Immune-related AEs will be tabulated using investigator-reported irAEs. .

Infusion related AEs will be tabulated using infusion-related reactions as reported by the investigators.

The following summaries by either SOC and PT or by PT and by toxicity grade will be provided. Summaries will be sorted by decreasing incidence of PT (within SOC, if applicable).

- TEAEs by SOC and PT, and by PT
- TEAEs by relationship to study drug, toxicity grade, SOC, and PT
- Drug-related TEAEs by SOC and PT, and by PT
- TEAEs leading to permanent treatment discontinuation by PT
- TEAEs leading to death by PT
- Drug-related TEAEs leading to permanent treatment discontinuation by PT
- Drug-related TEAEs leading to death by PT
- Serious TEAEs by SOC and PT, and by PT
- Serious TEAEs by relationship to study drug and toxicity grade, by SOC and PT
- Drug related serious TEAEs by SOC and PT, and by PT
- irAEs by SOC and PT, and by PT
- irAEs by relationship to study drug, toxicity grade, SOC, and PT
- Infusion-related TEAEs by SOC and PT, and by PT
- Infusion-related TEAEs by relationship to study drug, toxicity grade, SOC, and PT
- Laboratory abnormalities worsening (in at least one on-study measurement, relative to baseline) by NCI-CTCAE v4.03 criteria.
- ALT, AST, or bilirubin normal at baseline but with elevations $\geq 2 \times$ ULN.

The overall summary of will be reported by age (age < 55 vs age ≥ 55 , age < 65 vs age ≥ 65 , and age < 75 vs age ≥ 75), by race group including at least 5 subjects (groups < 5 subjects will be reported summarily as “Other”, patients treated in France who did not report race will be summarized as “Not reported (France)”), region (US vs EU vs other), and by normal vs abnormal creatinine and bilirubin levels at baseline.

In addition, the overall summary of AE incidence per month of drug exposure will be presented. Such a summary will report #patients/(total time of exposure in months) and #AEs/(total time of exposure in months.)

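### AE rates per month of drug exposure have no defined denominator; on the only measure the SAP offers, the #AEs rate is overstated and the #patients rate can err either way

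*SAP*

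**What the plan says.** SAP 7.6.2 states that "the overall summary of AE incidence per month of drug exposure will be presented" and gives the formula: "Such a summary will report #patients/(total time of exposure in months) and #AEs/(total time of exposure in months". It does not define the time of exposure, and it does not say whether the count is of all TEAEs, related TEAEs, immune-related AEs or something else.

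The one measure of time under SAP 7.6.1 Drug Exposure is "Duration of treatment (week), calculated as: (last dose date – first dose date + 1)/7". It stops on the day of the last dose.

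The counting windows run past that day:

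- The on-treatment period in SAP 5.3 continues, "i.e., until 35 days from the last dose) or end of study, whichever occurs first".
- The extended period in SAP 5.4 runs "through 90 days after the last dose of study treatment or end of study, whichever occurs first". SAP 7.6.2 applies it to immune-related events: "Immune-related AEs will be considered TEAEs during the extended on-treatment period". It also applies it to all TEAEs in a sensitivity analysis.
- The main TEAE definition reads: "TEAEs are AEs with onset during or after administration of first dose, or the worsening of a pre-existing condition during the on-treatment period". Grammatically, the on-treatment limit attaches only to worsening of pre-existing conditions.

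Protocol 8.3.4 has a different on-treatment period. It ends 30 days after the last dose or the day before new anticancer therapy, whichever is first.

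**The concern.** A rate per unit of time needs events and time drawn from the same period. If exposure time is taken from SAP 7.6.1, events after the last dose enter the numerator and the time in which they arose is left out of the denominator. A subject with one dose adds 1 day of exposure against a 36-day counting window. The SAP expects such events: it gives late toxicities as its reason for extending the immune-related window.

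The #patients version has a second defect. Each patient counts once, but her full exposure stays in the denominator, including time after her first event, when she can no longer add to the count. That pulls the rate down, against the first effect.

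At stake is the meaning of a descriptive safety figure in an analysis meant to support a licence application (SAP 4.2). Because the denominator is undefined, two programmers could produce materially different rates from the same data.

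**Working it through.** The documents state no AE rate and no expected treatment duration, so there is no figure of the plan's to reproduce.

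**Inputs.** Exposure per subject: last dose date minus first dose date plus 1 (SAP 7.6.1). Days counted after the last dose: w = 35 (SAP 5.3) or 90 (SAP 5.4). Dosing every 14 days (SAP 7.6.1). One month = 30.4375 days (SAP 7.2). Maximum treatment 24 months (protocol 5.4.1.1). Mean duration D, the relative post-dose rate f and the first-event hazards below are assumptions.

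**#AEs rate.** With on-treatment event rate r and post-dose rate f·r, expected events over N subjects are r·N·D + f·r·N·w. Dividing by exposure N·D gives r·(1 + f·w/D). Dividing by person-time in the matching window removes the mismatch, and with f = 1 it returns r. The overstatement relative to the on-treatment rate is therefore 1 + f·w/D. Only the mean of D matters.

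With f = 1 and D = 3 months = 91.3 days: 1 + 35/91.3 = 1.38 and 1 + 90/91.3 = 1.99. In the same way:

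| Assumed mean D | w = 35, f = 1 | w = 90, f = 1 | w = 35, f = 0.5 | w = 90, f = 0.5 |
|---|---|---|---|---|
| 3 months | 1.38 | 1.99 | 1.19 | 1.49 |
| 6 months | 1.19 | 1.49 | 1.10 | 1.25 |
| 12 months | 1.10 | 1.25 | 1.05 | 1.12 |
| 24 months (maximum) | 1.05 | 1.12 | – | – |

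The factor is 1 only if no counted AE starts after the last dose. If one total mixes immune-related AEs to 90 days with other TEAEs to 35 days, its factor at f = 1 lies between the two columns.

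**#patients rate.** Take six doses on schedule: exposure is 14 × 5 + 1 = 71 days = 2.33 months, and the window is 71 + 35 = 106 days = 3.48 months. With a constant first-event hazard h per month, the planned rate is (1 − exp(−3.48h))/2.33. First events divided by time to first event or end of window would give h.

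- h = 0.5: (1 − 0.175)/2.33 = 0.35 per month, or 0.71 times the matched rate. Too low.
- h = 0.02: (1 − 0.933)/2.33 = 0.029 per month, or 1.44 times the matched rate. Too high.

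A simulation with exponential treatment durations capped at 24 months, 14-day dosing, constant hazard and the 35-day window gives these ratios of planned to matched rate:

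| Mean exposure | h = 0.02 | h = 0.1 | h = 0.5 | h = 1.0 |
|---|---|---|---|---|
| about 2.8 months | 1.33 | 1.08 | 0.54 | 0.32 |
| about 5.7 months | 1.08 | 0.75 | 0.30 | 0.16 |

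The direction changes with the frequency of the event and the length of treatment.

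**The case against.** The strongest reply is that the SAP nowhere equates time of exposure with the SAP 7.6.1 duration, and nowhere says which AEs enter the rate. The mismatch is inferred, so a reader who calls the formula wrong as written goes too far. That stands: the formula is undefined, and mismatched on the only measure available.

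The size is also open to challenge. The documents give no treatment duration, and f = 1 over a fully observed window may be too high. Under protocol 7.2.1, AE reporting runs to 90 days after the last dose or the start of new anticancer treatment, and after the safety follow-up visit only treatment-related AEs are documented. Both SAP windows are also cut at end of study. These points lower the factors, particularly at 90 days, but do not bring them to 1. In the other direction, the TEAE wording could be read as setting no end date for new-onset events. The separate SAP listings of AEs after the on-treatment period suggest that this is not intended.

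A reader might infer three further things that the documents do not support:

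- That both rates are inflated. The #patients rate need not be, as shown above.
- That subgroups stopping early will look more toxic. SAP 7.6.2 lists its subgroups for the overall AE summary and then adds the per-month summary separately. Per-month rates by subgroup are not clearly planned.
- That the rates cannot be compared with other anti-PD-1 data. That depends on how those sources computed theirs, which the documents do not show.

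Finally, Phase 2 has a single arm, and subject and event counts are tabulated anyway. That limits the consequence but does not repair the rate.

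**Conclusion.** The point holds in a limited form. The denominator and the counted events are undefined. If exposure is first to last dose, the #AEs rate is overstated by 1 + f·w/D. For assumed mean durations of 3 to 12 months and f = 1, that is 1.38 down to 1.10 for the 35-day window and 1.99 down to 1.25 for the 90-day window; the excess halves at f = 0.5. The 90-day figures apply only if a per-month rate is produced on that window. These are scenarios, not estimates for this trial.

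The #patients rate is not a valid incidence rate under this definition, and its bias has no fixed sign: too high for rare events, usually too low for common ones such as any TEAE. A statement that the planned rates are all inflated, or that all would fall once corrected, would be wrong.

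The summary is descriptive. No endpoint, test or sample-size figure depends on it.

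**What to change.** In SAP 7.6.2:

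1. Name the AE set and the window for each rate. Use one window per rate; if immune-related AEs are counted to 90 days, report them separately or put the whole total on one window.
2. Divide #AEs by person-time in that same window: first dose to last dose plus 35 (or 90) days, cut at end of study, death or data cutoff.
3. For #patients, stop each subject's time at her first counted event.
4. Reconcile the SAP's 35 days with the 30 days or new-therapy limit in protocol 8.3.4. The SAP windows have no new-therapy cut. If time is cut at new anticancer therapy, drop later events from the numerator as well; cutting time alone would create a new mismatch.

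The cost is a few lines of SAP text and a small programming change, with no new data. The reported figures will shift: #AEs rates down, #patients rates up or down.
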